AE = adverse event; CGI = Clinical Global Impression; CSF = cerebrospinal fluid; ██████████ CTT = Color Trails Test; ECG = electrocardiogram; ██████████ LNS = Letter-Number Sequencing; LP = lumbar puncture; MDS-UPDRS = Movement Disorder Society-sponsored revision of the Unified Parkinson's Disease Rating Scale; MoCA = Montreal Cognitive Assessment; MRI = magnetic resonance imaging; NE = neurological examination; NSAEs = Non-Serious Adverse Events; PK = pharmacokinetic; QoL = quality of life; PSP = Progressive Supranuclear Palsy; PSPRS = Progressive Supranuclear Palsy Rating Scale; RBANS = Repeatable Battery for the Assessment of Neuropsychological Disease Severity; ██████████ SAEs = serious adverse events; SEADL = Schwab and England Activities of Daily Living scale; ██████████; WOCBP = women of childbearing potential.

^a Weeks 68, 72, 80, 84, 92, 96, 104, 108, 116, 120, 128, 132, 140, 144, 152, 156, 164, 168, 176, 180, 188, and 192 may qualify for home visits if appropriate. See Section 5.1.4 for details.

^b Participants who discontinue study treatment during the open-label extension period of the study (after Week 52) but remain enrolled in the study will be expected to complete scheduled safety and efficacy evaluations at Weeks 64, 76, 88, 100, 112, 124, 136, 148, 160, 172, 184, and 196.

^c Sample to be collected predose.

^d This 30-day assessment of AEs/SAEs may be done by phone if no visit occurs.

CONFIDENTIAL

The information contained herein may not be used, disclosed, or published without the written consent of Biogen MA Inc.

Table 4: Quantitative Assessment Procedural Outline for the Extension Period Substudy

Quantitative Movement Assessments	Substudy Enrollment in the Open-Label Extension Period		
	Baseline Visit ^a	Three-Month Follow-Up Visit ^b	Six-Month Follow-Up Visit ^b
In-Clinic Assessments			
Orthostatic vitals	X		
Visual acuity	X		
Joint-position test	X		
Strength test for hip flexion and knee extension	X		
Sway	X	X	X
Gait	X	X	X
Timed chair stands	X	X	X
Instrumented push and release test	X	X	X
Toe taps	X	X	X
Wrist rotations	X	X	X
In-Home Assessments			
Falls ^c		X	

QMA = quantitative movement assessments

^a The QMA substudy baseline visit will start after participants sign the informed consent form and are eligible to enroll in the substudy.

^b Two follow-up visits will be conducted at 3 and 6 months after the baseline visit of the QMA substudy.

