3.2 Analysis Period

Depending on the purpose, different analyses will be conducted on the following study periods:

1. **OLE period**. Only data in the OLE period will be included in these analyses. This OLE analysis period will be applied to all the AE analyses, and the analyses will include all subjects who were dosed in the OLE period.
2. **Placebo-controlled and OLE period**. All the data in the placebo-controlled and OLE periods will be included in these analyses. This analysis period will be applied to all efficacy analyses. The analyses will include all subjects who were dosed in the study including those who did not enroll into the OLE period.
3. **Active treatment (placebo-controlled and OLE) period**. The active treatment period is defined as the study period(s) in which a subject received BIIB092. For early start subjects, all data from placebo-controlled and OLE periods will be included. For late start subjects,

only data in the OLE period will be included. This analysis period will be applied to all safety analyses, and the analyses will include all subjects who were dosed in the study except for subjects who received only placebo in the placebo-controlled period and did not get dosed in the OLE period.

For a given output, both the analysis population and the analysis period will determine which subjects will be included. For example, the incidence table of adverse events in the OLE period will include subjects in the safety population for the OLE period, i.e., all randomized subjects who received at least one dose of study treatment in the OLE period. The incidence rate table of adverse events in the active treatment (placebo-controlled and OLE) period will include subjects in the safety population for the active treatment period, i.e., all randomized subjects who received at least one dose of treatment in the active treatment period. In this SAP we do not separately define the analysis population in each analysis period.

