6.1.4 Incidence, incidence proportion and incidence rate

- Incidence and incidence proportion will be provided in incidence proportion tables. Incidence is defined as the number of subjects who experienced an event. Incidence proportion is defined as the number of subjects who experienced an event divided by total number of subjects in the analysis population, i.e., percentage. Each subject will be counted only once within each category.

- Incidence and incidence rate will be provided in incidence rate tables. Two different kinds of incidence rate tables will be provided as appropriate for different analyses. Definitions are provided below.
 - Follow-up adjusted incidence rate (FAIR) – defined as the number of subjects with an event divided by the total follow-up time among the subjects in the analysis population (e.g., incidence rate per 100 subject-years). The total follow-up time (subject-years) is the sum of all subjects' follow-up time, where a subject's follow-up time is calculated as the number of days (inclusive) from first dose of treatment until the last day on study divided by 365.25. For active treatment period analyses, the first dose of treatment is considered the first dose received in the study period (PC or OLE) in which a subject first receives BIIB092. Each subject will be counted only once within each category.
 - Exposure-adjusted incidence rate (EAIR) – defined as the number of subjects with an event divided by the total exposure adjusted follow-up time (i.e. total time at risk for the event) among the subjects in the analysis population (e.g., incidence rate per 100 subject-years). The exposure adjusted follow-up time (time at risk for the event) for a subject is the time from the first dose of study drug in the first BIIB092 dosing period (PC or OLE) to the initial occurrence of the event for subjects who experienced the event, and is the time from first dose of study drug in the first BIIB092 dosing period to the end of follow-up (the last day on study) for subjects who did not experience the event. The total time at risk is the sum of all subjects' time at risk. Each subject will be counted only once within each category.

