6.2.5 Infusion reactions

Infusion reactions will be identified through 1) temporal association, defined as those events which occur on the day of an infusion or the subsequent two calendar days after an infusion; and 2) through a custom MedDRA search of preferred terms. The list of custom MedDRA search terms can be found in Appendix 11.2. A serious infusion reaction is a serious adverse event which is identified by one or both methods.

For the OLE period, an overall summary of infusion reactions will be provided with the number of subjects (n, %) with any infusion reaction; with any infusion reaction identified by temporal association only; with any infusion reaction identified through the custom search only; and any infusion reaction identified through both methods. Additionally, the following incidence proportion tables will be provided for the OLE period:

1. Infusion reactions (temporal association or custom search) by SOC and PT
2. Serious infusion reactions (temporal association or custom search) by SOC and PT
3. Infusion reactions (temporal association or custom search) for subjects with and without positive treatment emergent ADAs by PT
4. Serious infusion reactions (temporal association or custom search) for subjects with and without positive treatment emergent ADAs by PT
5. Infusion reactions that occurred in temporal association to an infusion by physical location of infusion (in-clinic vs. home) by SOC and PT
6. Serious infusion reactions that occurred in temporal association to an infusion by physical location of infusion (in-clinic vs. home) by SOC and PT
7. Infusion reactions identified through custom search criteria by PT
8. Infusion reactions (temporal association or custom search) by 12-week intervals by PT

Positive treatment emergent ADA will be based on the definition in Section 8 using the integrated placebo-controlled and open label extension data.

An exposure adjusted incident rate table for infusion reactions will be provided for the active treatment (placebo-controlled and OLE) period.

Additionally, the following incidence proportion tables will be provided for the active treatment (placebo-controlled and OLE) period:

1. Infusion reactions that occurred in temporal association to an infusion by physical location of infusion (in-clinic vs. home) by SOC and PT
2. Serious infusion reactions that occurred in temporal association to an infusion by physical location of infusion (in-clinic vs. home) by SOC and PT

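### The exposure-adjusted infusion-reaction rate counts follow-up after infusions have stopped as time at risk, so the rate while on BIIB092 is understated

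*SAP*

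**What the plan says.** OLE SAP 6.1.4 defines the exposure-adjusted incidence rate (EAIR) as subjects with an event divided by the "total exposure adjusted follow-up time (i.e. total time at risk for the event". A subject with the event contributes time to first occurrence. Otherwise the clock runs "to the end of follow-up (the last day on study) for subjects who did not experience the event".

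OLE SAP 6.2.5 applies this rate to infusion reactions: "An exposure adjusted incident rate table for infusion reactions will be provided for the active treatment (placebo-controlled and OLE) period". It sets no other end to the clock. It identifies reactions in two ways: by timing, as "those events which occur on the day of an infusion or the subsequent two calendar days after an infusion", and "through a custom MedDRA search of preferred terms" with no time limit.

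Follow-up without infusions is planned. Protocol Table 2 (footnote c) schedules placebo-period stoppers who remain enrolled through Week 52. Table 3 (footnote b) says that those who stop in the extension "but remain enrolled in the study will be expected to complete scheduled safety and efficacy evaluations". Protocol 8.2 continues adverse event collection to the end of study or withdrawal.

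The active treatment period covers all dosed subjects "except for subjects who received only placebo in the placebo-controlled period and did not get dosed in the OLE period" (OLE SAP 3.2, Analysis Period).

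Two other places set an end to exposure. Protocol 17.4.2 closes the cumulative BIIB092 safety data 30 days after the last dose. Section 4.3 of the placebo-controlled (PC) SAP counts each dose as 28 days of exposure and separately measures time on study beyond that.

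**The concern.** The denominator does not match its label. From the third day after the last infusion, the temporal method cannot register an event, yet an event-free subject who stays enrolled keeps adding person-time. That time can only lower the rate. The table is meant to show how often BIIB092 infusions lead to reactions, and its error favours the drug.

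The two groups also collect infusion-free time differently. Early start keeps every subject who stopped BIIB092 in the placebo-controlled period. Late start admits only subjects dosed in the extension. A side-by-side reading of the two rates could therefore mix reaction risk with retention after stopping.

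**Working it through.** The plan states no infusion-reaction rate and no off-treatment person-time, so there is no figure to reproduce. The check is of direction and plausible size.

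**Inputs**
- Infusions every 28 days, 13 in the double-blind period (Protocol 5.1.1); 28 days of exposure per dose (PC SAP 4.3).
- Fraction *f* who stop but stay: 5%, 10%, 15% or 25%. This is an assumption. The 25% is borrowed from the anticipated dropout in Protocol 17.1, which is not a stop-but-stay rate.
- Early start 26 cycles, late start 13 cycles (assumption). Stopping falls at random among 13 infusions, so on average 7 cycles are dosed and 6 of the 13 are not.
- Risk 0.5% per infusion (assumption): 0.005 × 365.25 / 28 = 6.5 per 100 subject-years while dosed.

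**Formula.** Infusion-free time adds nothing to the numerator, so shortfall = off-infusion time / total time. This ignores the stop at first event.
- A. Early start, placebo-period stoppers followed to Week 52: 6f / [13f + 26(1 − f)]
- B. Early start, stoppers followed for all 26 cycles: 19f / 26
- C. Late start, same stopping over 13 cycles: 6f / 13

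| f | A | B | C |
|---|---|---|---|
| 5% | 1.2% | 3.7% | 2.3% |
| 10% | 2.4% | 7.3% | 4.6% |
| 15% | 3.7% | 11.0% | 6.9% |
| 25% | 6.6% | 18.3% | 11.5% |

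Simulations that also stop the clock at the first event give 1.2%, 2.5%, 3.9% and 6.9% for A; 4%, 8%, 11% and 19% for B; and 2.3% to 11.7% for C. At f = 25%, a true 6.5 per 100 subject-years would be reported as about 6.1 (6.5 × 0.931), 5.3 and 5.7 (6.5 × 0.883).

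**Which group?** A and B include no early-start stopping in the extension. If the same fraction of completers stop over 13 extension cycles, case A becomes [6f + 6f(1 − f)] / [13f + 26(1 − f)] = 6f(2 − f) / [13(2 − f)] = 6f/13, which equals C. The groups are then diluted equally.

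A shorter extension tilts the balance to early start, and OLE SAP 5.3 expects few subjects at Week 100. Separate simulations assumed 10% or 25% stopping per year, 25% to 100% of them staying, and a mean extension of 0.25 or about 0.46 year. Against a clock ended at last dose + 30 days, the shortfall was about 1% to 19% in early start and 0.2% to 7% in late start, larger in early start in every run. With an extension beyond about a year and follow-up of placebo-period stoppers ending at Week 52, the order can reverse.

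**Where to cut.** Ending at last infusion + 2 days discards most of the last dosing interval. The rate is then inflated by 28n / [28(n − 1) + 2] for n infusions:
- n = 6: 168/142 = 1.18, giving 7.7 against a true 6.5
- n = 26: 728/702 = 1.04, giving 6.8

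The inflation depends on the number of infusions, so it would create a new difference between groups. A full 28-day window gives a factor of 1.

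**The case against.** The strongest case against is that this is one descriptive safety table with no planned early-versus-late test, and that the effect is small if few subjects stay after stopping. Both statements stand. They limit the size and the consequence, but the denominator still does not match its label.

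Four stronger readings are tempting, and the documents do not support them.

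- **No infusion reaction can occur after infusions stop.** This is exact only for the temporal method. The term search has no time limit, and Appendix 11.2 includes terms such as cytokine storm. Most listed terms are infusion, administration or injection reactions, so few late events are expected.
- **Early start will look safer than late start.** This needs late-start subjects never to stop and stay, but Table 3 footnote b covers extension stoppers in both groups. The order turns on stopping, retention and extension length, none of which is given.
- **The shortfall passes 10% once about 15% stop.** That holds only if placebo-period stoppers are followed for the full 26 cycles (case B). Protocol 5.1.1 offers the extension to those completing double-blind treatment, and Table 2 footnote c ends the stoppers' schedule at Week 52. Protocol 5.1.5 does speak of evaluations to the end of the study, so B is kept as an upper bound. In case A, 10% is not reached even at 25% stopping.
- **This is the only follow-up-adjusted summary of these events.** The follow-up-adjusted tables in OLE SAP 6.2.3 cover all adverse events by preferred term. The special-interest EAIR table in 6.2.4 includes several of the same terms (Appendix 11.1). Both run to the last day on study, so they do not supply the missing on-treatment rate.

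**Conclusion.** The point holds. The direction follows from the definitions: infusion-free follow-up enlarges the denominator and, under the temporal method, cannot enlarge the numerator. The rate while on BIIB092 is therefore understated wherever event-free subjects stop but stay.

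The size rests on assumptions because the documents give no stop-but-stay rate. For 5% to 25%, on 26 and 13 cycles, it is about 1% to 7% in early start with follow-up of placebo-period stoppers ending at Week 52, up to about 19% with follow-up to the data cut, and about 2% to 12% in late start with equal stopping. The early-start range counts placebo-period stopping only and would be larger with a shorter extension. Which group is more affected is not established. This is a modest but correctable bias in a descriptive table.

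**What to change.** In OLE SAP 6.2.5, for the infusion-reaction EAIR table only, end time at risk at the earliest of:
- the first reaction;
- the last BIIB092 infusion plus one full exposure window, either 30 days to match Protocol 17.4.2 or the 28 days per dose of PC SAP 4.3, with one chosen and stated;
- the last day on study.

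Do not use last infusion + 2 days. List separately any custom-search event with onset after the window.

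Optionally, add subjects with reactions, or reactions, per 100 BIIB092 infusions given. This avoids the person-time question and lets the groups be read on the same scale.

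Infusion records are already collected. The cost is a sentence of SAP wording, one revised table and a slightly less favourable reported rate.

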6.3 Clinical Laboratory Data

The following scheduled clinical laboratory parameters are to be assessed:

| | |
|--|---|
| Hematology | |
| Red blood cell count | |
| Hemoglobin | |
| Hematocrit | |
| Total leukocyte count, including differential | |
| Platelet count | |
| Serum Chemistry | |
| Aspartate aminotransferase (AST) | Total Protein |
| Alanine aminotransferase (ALT) | Albumin |
| Total bilirubin | Sodium |
| Direct bilirubin | Potassium |
| Alkaline phosphatase | Chloride |
| Lactate dehydrogenase (LDH) | Calcium |
| Creatinine | Phosphorus |
| Blood Urea Nitrogen (BUN) | Magnesium |
| Uric acid | Creatine kinase |
| Glucose | Thyroid stimulating hormone (TSH)- screening only |
| Urinalysis | |
| Protein | |
| Glucose | |
| Blood | |
| Leukocyte esterase | |
| Specific gravity | |
| pH | |
| Microscopic examination of the sediment if blood, protein or leukocyte esterase are positive on the dipstick | |
| Serology | |
| Serum for hepatitis C antibody, hepatitis B surface antigen (screening only) | |
| Other Analyses | |
| INR | |
| Prothrombin Time (PT) | |

| |
|---|
| Hemoglobin A1C (HbA1C)- screening only |
| Pregnancy test (WOCBP only: screening, predose, discharge). |
| Follicle stimulating hormone (FSH) (screening only for women) |
| |
| |
| |

Summaries of clinical laboratory data will be performed for scheduled laboratory parameters, excluding CSF parameters. Listings of individual laboratory measurements by subjects for all the parameters, both scheduled and unscheduled, will be provided as per the placebo-controlled SAP.

Analysis period and analysis displays

The analysis period and analysis displays are defined in Section 6.1.2.

6.3.1 Quantitative analyses

Actual values, change from baseline and percent change from baseline will be summarized by visit for hematology, blood chemistry, coagulation (INR and prothrombin time), and the urinalysis parameters specific gravity and pH (actual values over time only), for all the visits in the active treatment (placebo-controlled and OLE) period. Number of evaluable subjects, mean, standard deviation, 25% and 75% quartiles, min and max values will be presented at each visit.

Plots of mean values (with standard error) for numeric laboratory parameters at each visit for all the visits in the active treatment (placebo-controlled and OLE) period will be provided. Mean values at timepoints where $n < 20$ will not be plotted.

Visit windows for by visit summaries

For laboratory by visit summaries, the analysis visit should be defined using visit windows (see Tables 7 and 8 below).

Table 7 Visit Windows for Laboratory by Visit Summaries for BIIB092 Early Start Subjects

| Analysis visit | Target visit day | Analysis visit window |
|-----------------------|-------------------------|---|
| Baseline | 1 | Most recent non-missing value prior to the first dose of study drug in the PC dosing period |
| Week 4 | 29 | [1 (post-dose only), 42] |
| Week 8 | 57 | [43, 70] |
| Week 12 | 85 | [71, 126] |
| Week 24 | 169 | [127, 210] |
| Week 36 | 253 | [211, 294] |

| Analysis visit | Target visit day | Analysis visit window |
|---|-------------------------|------------------------------|
| Week 48 | 337 | [295, 350] |
| Week 52 | 365 | [351, 406] |
| Week 64 | 449 | [407, 490] |
| Week 76 | 533 | [491, 616] |
| Week 100 | 701 | [617, 784] |
| Week 124 | 869 | [785,952] |
| Week 148 | 1037 | [953,1120] |
| Week 172 | 1205 | [1121,1288] |
| Week 196 | 1373 | >=1289 |
| Analysis Visit, Target visit day and Analysis visit window are calculated relative to the day of first dose of study drug (BIIB092 or placebo) in the PC dosing period. | | |

Table 8 Visit Windows for Laboratory by Visit Summaries for BIIB092 Late Start Subjects

| Analysis visit | Target visit day | Analysis visit window |
|--|-------------------------|--|
| OLE Baseline | 1 | Most recent non-missing value prior to the first dose of study drug in the OLE dosing period |
| Week 12 | 85 | [1 (post-dose only), 126] |
| Week 24 | 169 | [127 252] |
| Week 48 | 337 | [253, 420] |
| Week 72 | 505 | [421, 588] |
| Week 96 | 673 | [589, 756] |
| Week 120 | 841 | [757, 924] |
| Week 144 | 1009 | >=925 |
| Analysis Visit, Target visit day and Analysis visit window are calculated relative to the day of first dose of study drug in the OLE dosing period.. | | |

6.3.2 Qualitative analyses

For all qualitative analyses, all values will be included (not just the “analyzed record” within each visit window in the quantitative analyses).

Shift analyses

Laboratory data will be summarized using shift tables where appropriate for the active treatment (placebo-controlled and OLE) period. Each subject’s hematology, blood chemistry, coagulation and urinalysis (excluding microscopic examination) numeric values will be flagged as “low”,

“normal”, or “high” relative to the normal ranges of the central laboratory or as “unknown” if no result is available. Each subject’s urinalysis categorical values (parameters of protein, glucose, blood, and leukocyte esterase) will be flagged as “abnormal” if positive, “normal” if negative, or “unknown” if no value is available.

For each parameter, the analysis will be based on subjects with at least one post-baseline value. Shifts from baseline to high/low status will be presented for hematology, blood chemistry and urinalysis (specific gravity and pH) numeric parameters, and shifts from baseline to abnormal (positive) will be presented for urinalysis categorical parameters (protein, glucose, blood, and leukocyte esterase). Shift to low includes normal to low, high to low, and unknown to low; shift to high includes normal to high, low to high, and unknown to high. Subjects need to have at least one post-baseline evaluation and a baseline value either unknown or not low/high/abnormal (including missing) in order to be included in the analysis.

For early start subjects, the placebo-controlled baseline will be used and shifts that occurred in either placebo-controlled or OLE period will be included. For late start subjects, the active treatment period baseline will be used and shifts that occurred in the OLE period based on the active treatment period baseline will be included.

Potentially Clinically Significant laboratory abnormalities analyses

For hematology, blood chemistry and urinalysis, the number of subjects with potentially clinically significant (PCS) laboratory abnormalities post-baseline will be summarized for the parameters provided in Table 9 for the active treatment (placebo-controlled and OLE) period.

Subjects need to have at least one post-baseline evaluation in the active treatment period and a baseline value not potentially clinically significant (including missing) in order to be included in the analysis.

Same as the shift analysis, for early start subjects, the placebo-controlled baseline will be used and abnormalities that occurred in either placebo-controlled or OLE period will be included. For late start subjects, the active treatment period baseline will be used and the PCS abnormalities that occurred in the OLE period based on the active treatment period baseline will be included.

Table 9: Criteria to Determine Potentially Clinically Significant (PCS) Laboratory Abnormalities

| Clinical Laboratory Outlier Criteria | | |
|--------------------------------------|----------------------------|----------------------------|
| Parameter name | PCS Low | PCS High |
| HEMATOLOGY | | |
| White blood cells | <3.0 x 10 ⁹ /L | >16 x 10 ⁹ /L |
| Lymphocytes | <0.8 x 10 ⁹ /L | >12 x 10 ⁹ /L |
| Neutrophils | <1.5 x 10 ⁹ /L | >13.5 x 10 ⁹ /L |
| Monocytes | N/A | >2.5 x 10 ⁹ /L |
| Eosinophils | N/A | >1.6 x 10 ⁹ /L |
| Basophils | N/A | >1.6 x 10 ⁹ /L |
| Red blood cells | ≤3.5 x 10 ¹² /L | ≥6.4 x 10 ¹² /L |
| Hemoglobin - Females | ≤95 g/L | ≥175 g/L |
| Hemoglobin - Males | ≤115 g/L | ≥190 g/L |
| Hematocrit - Females | ≤0.32 L/L | ≥0.54 L/L |
| Hematocrit - Males | ≤0.37 L/L | ≥0.60 L/L |

| Clinical Laboratory Outlier Criteria | | |
|---|---------------------------|-----------------------------|
| Parameter name | PCS Low | PCS High |
| Platelet count | $\leq 75 \times 10^9/L$ | $\geq 700 \times 10^9/L$ |
| BLOOD CHEMISTRY | | |
| Alanine aminotransferase (ALT) | N/A | $> 3 \times \text{ULN}$ |
| Aspartate aminotransferase (AST) | N/A | $> 3 \times \text{ULN}$ |
| Alkaline phosphatase (ALP) | N/A | $> 3 \times \text{ULN}$ |
| Total bilirubin | N/A | $> 1.5 \times \text{ULN}$ |
| Blood urea nitrogen (BUN) | N/A | $\geq 10.7 \text{ mmol/L}$ |
| Creatinine | N/A | $\geq 176.8 \text{ umol/L}$ |
| Sodium | $\leq 126 \text{ mmol/L}$ | $\geq 156 \text{ mmol/L}$ |
| Potassium | $\leq 3 \text{ mmol/L}$ | $\geq 6 \text{ mmol/L}$ |
| Chloride | $\leq 90 \text{ mmol/L}$ | $\geq 118 \text{ mmol/L}$ |
| Glucose | $\leq 2.2 \text{ mmol/L}$ | $\geq 9.7 \text{ mmol/L}$ |
| Calcium | $\leq 2 \text{ mmol/L}$ | $\geq 3 \text{ mmol/L}$ |
| Phosphorus | $\leq 0.6 \text{ mmol/L}$ | $\geq 1.7 \text{ mmol/L}$ |
| Albumin | $\leq 25 \text{ g/L}$ | $\geq 625 \text{ g/L}$ |
| Total protein | $\leq 45 \text{ g/L}$ | $\geq 100 \text{ g/L}$ |
| URINALYSIS | | |
| Glucose | N/A | $\geq 1000 \text{ mg/dL}$ |
| Protein | N/A | $\geq 100 \text{ mg/dL}$ |
| ULN = upper limit of normal | | |

Potential serious hepatotoxicity

Potential serious hepatotoxicity is defined as ALT or AST $> 3 \times \text{ULN}$ and total bilirubin $> 2 \times \text{ULN}$ at any time post-baseline in the active treatment (placebo-controlled and OLE) period, not necessarily concurrent. A scatterplot of the maximum post-baseline ALT or AST value relative to ULN and maximum post-baseline total bilirubin value relative to ULN (not necessarily concurrent) for each subject will be provided. A line plot of ALT, AST, ALP and total bilirubin values over time for subjects with potential serious hepatotoxicity will be provided. In addition, subjects with ALT $> 1 \times \text{ULN}$, $> 3 \times \text{ULN}$, $> 5 \times \text{ULN}$, $> 10 \times \text{ULN}$ or $> 20 \times \text{ULN}$, subjects with AST $> 1 \times \text{ULN}$, $> 3 \times \text{ULN}$, $> 5 \times \text{ULN}$, $> 10 \times \text{ULN}$ or $> 20 \times \text{ULN}$, subjects with total bilirubin $> 1 \times \text{ULN}$ or $> 2 \times \text{ULN}$, subjects with ALP $> 1 \times \text{ULN}$ or $> 1.5 \times \text{ULN}$, and subjects with AST or ALT $> 3 \times \text{ULN}$ post-baseline accompanied by concurrently elevated total bilirubin $> 1.5 \times \text{ULN}$ or $> 2 \times \text{ULN}$ will be presented. Concurrent is defined as on the same day. A listing of subjects with potential serious hepatotoxicity will be provided as part of the analysis specified by the placebo-controlled SAP.

